**Developing an implementation strategy for post-concussion communication with  
low health literacy parents in the emergency department**

**NCT Number:** NCT04112914

**Document Date:** 4/29/2021

*Please note: Due to the smaller sample recruited we simplified our analytic plan to focus on primary outcomes and no subgroup comparisons.*

## 1. Objectives

### 1.1. Purpose, specific aims, or objectives:

The aims of this project are to:

**Aim 1:** Engage families and health care providers in: adapting the CDC's Acute Concussion Evaluation Care Guidelines to be readable/useable by families with low health literacy and developing an implementation strategy for communicating about this information and sharing this adapted handout with families who sought closed head injury care for their child in the emergency department (ED).

**Aim 2:** Assess how treatment-as-usual is being experienced by parents seeking care for their child post-closed head injury in the ED.

**Aim 3:** Assess the impact of strengthened post-closed head injury communication (as developed in Aim 1) on family adherence to evidence-based concussion management guidelines.

Aim 4: Ensure the study measures used in this study are valid and reliable- including ensuring that participants are not confused by question wording and that responses are correlated with other demographic, behavior, knowledge, and self-efficacy variables in predictable ways (e.g., to assess measure validity).

### 1.2. Hypotheses to be tested:

Aim 1: This research is qualitative and exploratory; our goal is to understand the perspectives of different stakeholders in order to adapt materials and develop an implementation strategy that better supports family adherence with evidence-based guidelines about post-concussion management following discharge from the ED.

Aims 2 and 3: We expect that families who receive the adapted education toolkit (Aim 3) will report greater understanding of evidence-based guidance and will be more prepared to adhere to evidence-based guidance post-closed head injury as compared to parents in the control condition.

Aim 4: This research is qualitative and exploratory; our goal is to develop and validate measures of concussion-related behaviors, knowledge, and self-efficacy. We aim to get feedback from adults to ensure that the survey questions for Aims 2 and 3 are easily understood and that the measures are valid and reliable.

## 2. Background

### 2.1. Relevant prior experience and gaps in current knowledge:

**Appropriate concussion management reduces concussion-related morbidity** Every year, more than one million U.S. youth are diagnosed with a concussion from sport or recreational activities. The Centers for Disease Control and Prevention's (CDC) recent Report to Congress on the Management of Traumatic Brain Injury in Children emphasizes that appropriate post-concussion management in the home, school and sport settings is critical for minimizing morbidity. During the symptomatic period post-injury, which can range from several hours to months, the brain experiences a metabolic cascade during which there is greater vulnerability to additional injury. Appropriate management is important for minimizing risk of subsequent injury and optimizing quality of life during recovery. Consensus guidelines recommend avoiding activities with a risk of contact or collision (e.g., sport) and, after a brief period of rest, moderating cognitive demands in the school and home setting in response to symptoms, under the guidance of a medical professional. **Parents are key partners in implementing evidence-based guidelines about post-concussion management in the home, school and sport settings.** This includes being observant for symptoms at home, interfacing with medical providers and academic personnel and ensuring the child does not return to sport prematurely

and risk greater injury. However, many parents lack knowledge about post-concussion management and struggle to achieve the necessary communication, decision-making, and planning to support their child's recovery. In part due to differences in post-concussion management behaviors, lower socioeconomic status youth are at elevated risk of experiencing poor health-related quality of life post-concussion. Consistent with broader patterns in health literacy, components of which include being able to access, understand and apply health-related information, concussion knowledge and information-seeking tends to be greater among more educated, affluent, non-Hispanic white parents. **There is thus a critical need to address knowledge translation to low health literacy parents to support post-concussion management behavior. For many families, the initial post-concussion visit in the emergency department (ED) is the sole point of clinical contact post-injury and a critical time for evidence-based knowledge translation.** Youth on Medicaid who seek medical attention post-concussion are most likely to do so in an ED. More than two thirds of pediatric patients seen post-concussion in the ED do not seek follow-up from a concussion specialist or primary care provider, due in part to inconsistent recommendations from ED providers and their lack of a medical home. This heightens the importance of knowledge translation to parents in the ED. However, there is substantial variability in whether the written discharge instructions parents receive are based on current consensus guidelines. **Existing evidence-based approaches to knowledge translation post-concussion are currently inadequate without adaptation to meet the needs of parents with low health literacy.** The CDC has developed the Acute Concussion Evaluation (ACE) Care Plan, a two-page handout for healthcare providers to share with families following their child's injury with information about returning to daily activities, return to school and return to sport. Sharing these materials has been recommended as part of an evidence-based clinical pathway for acute pediatric post-concussion evaluation and management and their utilization has been associated with improved youth outcomes. However, the short and densely-written fact sheet does not adhere to best practices for knowledge translation to low health literacy patients, such as giving the most important information first, using visuals where possible, limiting the number of messages and clearly stating the actions the reader should take. Additionally, the readability of the CDC ACE Care Plan handout is at a 10th grade level (Flesch Reading Ease=49.0, Flesch-Kincaid Grade Level=10.0), which is higher than recommended guidelines. Finally, these materials have not been translated into Spanish or any other language. **Thus, there is a need to adapt the CDC ACE Care Plan to meet the learning needs of parents with low health literacy and limited English proficiency (LEP). Well-designed written materials alone are not sufficient for effective knowledge translation that supports behavior change.** Among parents, recall of written discharge instructions from EDs post-concussion is greater when they are accompanied by a verbal discussion from nurses in the ED. This is consistent with a broader literature on educational strategies for families in healthcare settings, which recommends a provider-initiated discussion that includes a teach-back component to gauge understanding. Such a discussion can also help parents identify and address barriers to action beyond knowledge, such as how to access additional care if symptoms are not improving. However, only half of youth with sports-related concussion who sought care in the ED report having discussed discharge instructions with a healthcare provider. Such variable implementation disproportionately impacts lower SES families, as racial or ethnic minority families or families with limited education are less likely to ask questions of providers, and are less likely to have a teach-back style of patient education used in their clinical visit. More than half of physicians in ED settings have inadequate knowledge about post-concussion management and a systematic review of the training provided to ED physicians concluded that there is a need for improved training to optimize the dissemination and implementation of best practices for concussion management in this setting. **Existing approaches for discharge communication can be adapted to support implementation of evidence-based**

**parent education about concussion management.** The Agency for Healthcare Research and Quality (AHRQ) has developed a Re-Engineered Discharge (RED) Toolkit19(p2) to help optimize the discharge process in hospital settings that can be used as a foundation for acceptable and equitable implementation of the CDC ACE Care Plan. Core components of RED guidance related to family-provider communication include: (1) ensuring that written materials are easily understood and available in the family's preferred language, (2) ensuring there is satisfactory explanation of these materials, including an opportunity to ask questions, and (3) providing support in planning next steps for engaging in recommended behaviors19(p2). Ongoing quality improvement efforts at Seattle Children's Hospital have identified important opportunities for implementing RED communication guidelines, such as having nurses work with families to gauge understanding and plan next steps. **To realize improved discharge communication, ED providers (physicians and nurses) require: (1) access to evidence-based information about concussion management to share with parents post-injury and (2) support implementing such materials in their clinical setting.**

**2.2. Relevant preliminary data:**

See section 2.1

**2.3. Scientific or scholarly background:**

See section 2.1

**2.4. Prior approvals:**

N/A

**3. Study Endpoints**

**3.1. Primary and secondary endpoints:**

**Aim 1:** Recruitment of participants will occur until thematic saturation. For each participant, the endpoint will be the conclusion of the interview or focus group.

**Aim 2:** Recruitment will continue until 200 families agree to participate. For each family, participation will conclude after completing the two-week post-discharge survey.

**Aim 3:** Recruitment will continue until 200 families agree to participate. For most families, participation will conclude after completing the two-week post-discharge survey. For a subset of families, participation will conclude at the conclusion of the interview.

**Aim 4:** Recruitment will continue until thematic saturation. For each cognitive interviewing participant, the endpoint will be the conclusion of the cognitive interview. For each online survey participant, the endpoint will be the conclusion of the online survey.

**3.2. Primary or secondary safety endpoints:**

There are no primary or secondary safety endpoints for this research project.

**4. Drugs, Devices and Biologics**

**4.1. Manufacturer and name of all drugs, devices and biologics:**

N/A

**4.2. Description and purpose of all drugs, devices and biologics:**

N/A

**4.3. Regulatory status of all drugs, devices and biologics:**

N/A

**4.3.1. Drugs or Biologics:**

IND Exempt. Explain: [Click here to enter text.](#)  
 IND.

**4.3.2. Devices:**

IDE Exempt. Explain: [Click here to enter text.](#)  
 Abbreviated IDE / Non-Significant Risk. Explain: [Click here to enter text.](#)  
 IDE / Significant Risk.

**4.4. Plans to store, handle, and administer any study drugs, devices and biologics so they will be used only on subjects and be used only by authorized investigators:**

N/A

**5. Procedures Involved****5.1. Study design:****Aim 1:** Qualitative methodology, including interviews.**Aims 2 and 3:** Consecutive cohort design with randomization.**Aim 4:** (1) Cognitive interviewing (one-on-one interviews where participants talk through survey questions and identify challenging/confusing parts), and (2) cross sectional study, with data collected through anonymous online surveys.**5.2. Research procedures:**

**Aim 1:** This aim involves qualitative interviews, following a semi-structured questioning methodology, informed by an interview guide that will be iteratively and flexibly adapted based on emergent participant feedback. Interviews will be digitally recorded and transcribed verbatim, then coded for relevant themes using a thematic analysis approach. We will announce that the interview will be recorded at the beginning of each interview, and that announcement will be recorded. We will conduct a one-on-one interview with each parent and healthcare participant that will last approximately 45 minutes. Parent interviews will be conducted remotely (e.g., by phone or by video conferencing) or in person at SCH or the parent's house or a nearby community location (e.g., private room in public library). Healthcare provider interviews will be conducted remotely (e.g., by phone or by video conferencing) or in person in a private room at SCH. Interviews with parents will be conducted in their native language (English or Spanish). Spanish language interviews will be conducted by a research team member who is fluent in Spanish and is a Certified Bilingual staff member, with consent also obtained by this person. As part of parent data collection for Aim 1, all parents will complete the 3-item Brief Health Literacy Screen as part of a demographic questionnaire given prior to the start of the interview. For remote qualitative interviews, the same procedures will be followed, however, participants will be emailed the demographic questionnaire and information sheet and they will participate via an online platform (i.e. Zoom). Please see timeline (uploaded in "Other Attachments") for more information regarding the timing of Aim 1.

**Aims 2 and 3:** We will assign participants to the intervention and control groups using a consecutive cohort design with randomization. In the first data collection cohort (Aim 2), all participants will be assigned to the education-as-usual control condition. In the second cohort (Aim 3), participants will be

randomized to either the education toolkit intervention condition or treatment-as-usual control condition in a 2:1 ratio. For participants in the control group (Aim 2 and those randomized to control group in Aim 3), there will be no change to the nature of provider communication with families about closed head injury/concussion. Data will be collected about the experience that family's have seeking care in the ED for their child's closed head injury. For both Aims 2 and 3, survey data will be collected from parents at three time points: at initial ED visit before discharge, one day post-visit, and at 2-week follow-up. As part of parent data collection for Aims 2 and 3, all parents will complete the 3-item Brief Health Literacy Screen at the first time point of survey data collection. Please see timeline (uploaded in "Other Attachments" for more information regarding the timing of Aims 2 and 3.

For Aim 3 participants randomized to the intervention group, the parent education toolkit finalized in Aim 1 will be delivered by the study team. Based on feedback from qualitative interviews in Aim 1, the toolkit will consist of brief education from a member of the ED study team at enrollment, followed by asynchronous phone-based follow-up (audio/ voice and/or text). Parents will receive automated daily educational messages related to how they can provide recovery support to their children during the 2-week study period. Automated messages will be delivered via Twilio, by turning on the "initiate survey as SMS conversation" feature in REDCap. Parents will also receive reminders to schedule a follow-up appointment, with an option to receive tailored support from research staff to help with scheduling. A more detailed description and content of each toolkit component can be found in "Aim 3 Parent Education Toolkit Content" uploaded in "Other Attachments".

All patient materials will be available in both English and Spanish. Certified translations will be uploaded prior to use.

For both Aims 2 and 3, survey data will be collected from parents at three time points: immediately post-visit, one day post-visit, and at 2-week follow-up. A purposive subset of parents who complete all three surveys in Aim 3 will be invited to participate in optional one-on-one qualitative interviews. Interviews will be conducted remotely (e.g., by phone or video conferencing) and will be recorded. As part of parent data collection for Aims 2 and 3, all parents will complete the 3-item Brief Health Literacy Screen at the first time point of survey data collection.

**Aim 4:** (1) Cognitive interviewing: Parents will complete a one-on-one conversation with a research team member in or near the ED. In that conversation, they will be asked to read through a series of survey questions about parent behaviors, self-efficacy, and knowledge related to concussion and concussion management to help develop the final survey instrument for Aims 2 and 3 (a mock up of the cognitive interviewing survey instrument can be found in "Other Attachments"). Participants will then be asked to provide feedback about how they would think about answering these questions, with a particular focus on identifying anything that is confusing about the questions conceptually and any wording that is confusing or ambiguous. They will not be asked to answer questions about their personal health status or the health status of their children. All potential participants will complete the 3-item Brief Health Literacy Screen as part of screening, with stratified purposive recruitment among adequate and low health literacy parents until thematic saturation of survey feedback is reached. (2) Online surveys: Participants will complete online surveys built in REDCap with the survey link posted on the participant recruitment tool Amazon Mechanical Turk (or MTurk). The surveys will consist of behavior, belief, knowledge, and demographic questions that will help us validate the survey measures to be used in Aims 2 and 3. Participants will not be asked to answer questions about their personal health status or the health status of their children. Based on cognitive interview responses, we will post a subset of the survey questions on MTurk with potential corrected wording for clarity based on participant feedback. Participation in the online surveys will be voluntary and anonymous. A mockup of the online REDCap surveys can be viewed in "Other Attachments". Please see the study timeline (also uploaded in "Other Attachments") for more information regarding the timing of Aim 4.

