### 5.4. Data to be collected, including long-term follow-up data:

**Aim 1:** The goal of the parent interview will be to (1) explore their experiences with communication in the ED following their child's concussion and (2) provide critical feedback on the content and design of the CDC ACE Care Plan. The Cultural Treatment Adaptation Framework, will provide the foundation for the open-ended question guide for parents, with questions about the handout focusing on: (1) language and semantics, (2) use of culturally relevant examples, and 3) preferences for material delivery. The goal of the healthcare provider interviews will be to review the CDC ACE Care Plan handout and the RED Toolkit, and provide feedback about (1) barriers and facilitators to implementation in the ED and (2) the type of support (e.g., materials, training) that they believe would be helpful for implementation. CFIR^24 will provide the foundation for the open-ended question guide for healthcare providers, with a focus on individual characteristics (e.g., provider knowledge and self-efficacy), implementation toolkit characteristics, and aspects of the inner setting (e.g., time pressures in the busy ED, compatibility with existing communication networks and tools such as the EHR system) that may constrain implementation success.

**Aims 2 and 3:** Survey data will be collected from up to 200 parents at three time points: at initial ED visit before discharge, one day post-visit, and at 2-week follow-up. **Primary outcome.** Our primary outcome will be parenting behaviors at 2 week follow-up (emotional support and instrumental support). **Secondary outcomes.** Parent surveys at initial ED visit before discharge, one day post-visit, and two-weeks post visit will assess parent cognitions related to concussion management and proximal cognitions (concussion management knowledge and self-efficacy), parental anxiety related to concussion management, youth outcomes (health-related quality of life, post-concussion symptoms), the nature of provider-parent communication in the ED (e.g., did the parent have an opportunity to ask questions?), and additional

covariates (demographics and environmental conditions). In Aim 3 only, the parent surveys at 2 weeks post-visit will also include questions about their experiences with receiving the education toolkit.

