### 10.4. Power analysis:

**Aim 1:** This is a qualitative study and thus a power calculation is not appropriate.

**Aims 2 and 3:** With 200 participants per group (Aim 2 and Aim 3), we will have  $\geq 98\%$  power to detect a meaningful 20% difference in the proportion of parents receiving each specific component of the reach measure (Table 1), in Aim 2 vs. Aim 3 groups, after allowing for 10% attrition ( $\alpha=0.05$ ). For Health Literacy subgroup comparisons, we will have  $\geq 80\%$  power to detect a 20% difference, assuming 10% attrition.

**Aim 4:** This is an exploratory, primarily qualitative study and thus a power calculation is not appropriate.

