**Aims 2 and 3: Primary outcomes.** We will compare parenting behaviors (emotional support and instrumental support) at Time 3 between the two groups using chi-squared tests for each behavior and total proportion of behaviors. **Secondary outcomes.** For each group (control and intervention), the percentage of parents reporting receipt of specific discharge components will be calculated and compared. We will also compare rates across specific subgroups, including high vs. low health literacy parents and between parents who speak English at home vs. those who do not. These percentages will be compared across subgroups using chi-squared tests to assess statistical significance. We will also compare characteristics of subjects who (a) agree to participate vs. those who do not, and (b) participate throughout follow-up vs. any lost to follow-up. We will also conduct exploratory analyses of the mean change in parent cognitions related to concussion management (concussion management knowledge, parental anxiety, and behavioral self-efficacy) and child well-being scores (child PEDs-QL and PCSI) from Time 1 to Time 3, between the groups using t-tests, and plotting trajectories for each group. We will adjust analyses for child age, sex, baseline post-concussion symptoms/severity, as well as covariates not determined to be effect modifiers, if associated with outcome and distributions vary by treatment group. Missing data will be examined for patterns with covariates, sensitivity analyses used to assess impact of missing data on results and imputation used as appropriate to address missingness. **Parent experiences with enhanced education.** Survey data will be analyzed descriptively, with associations by insurance status, language, and gender assessed. For qualitative data, audio-recorded and transcribed interviews will be coded using a deductive content analytic approach using consensual qualitative research methods. First, two independent coders will review each interview transcript, applying codes from the CFIR, Communication Accommodation Theory, and USE-EBPI while remaining open to other emergent themes. They will then compare codes and agree on final codes using a process of deliberation and consensus.

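### The primary comparison mixes earlier, non-randomised Aim 2 parents into the control group, and no Aim 3-only randomised estimate, cohort term or drift check is named beside it

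*Combined protocol and SAP*

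**What the plan says.** Section 5.2 describes consecutive cohorts. All Aim 2 parents are controls and are not randomised; Aim 3 parents are randomised 2:1 to toolkit or usual care. The same section describes the controls as "For participants in the control group (Aim 2 and those randomized to control group in Aim 3". The hypothesis in section 1.2 sets toolkit families "as compared to parents in the control condition".

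Section 5.4 states: "Our primary outcome will be parenting behaviors at 2 week follow-up (emotional support and instrumental support". Section 14.1 says: "We will compare parenting behaviors (emotional support and instrumental support) at Time 3 between the two groups using chi-squared tests". The two groups are named in the next step, on secondary outcomes: "For each group (control and intervention), the percentage of parents reporting receipt of specific discharge components will be calculated and compared". On adjustment it says: "We will adjust analyses for child age, sex, baseline post-concussion symptoms/severity, as well as covariates not determined to be effect modifiers", the last of these only if they are associated with outcome and differ by treatment group. It does not name cohort or calendar time.

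Section 10.4 gives at least 98% power for a 20-point difference in "each specific component of the reach measure (Table 1), in Aim 2 vs. Aim 3 groups, after allowing for 10% attrition". The cover note adds: "Due to the smaller sample recruited we simplified our analytic plan to focus on primary outcomes and no subgroup comparisons".

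**The concern.** Randomisation protects only the toolkit versus control contrast within Aim 3. Once Aim 2 parents join the controls, any difference between cohorts that the planned covariates do not remove becomes part of the apparent toolkit effect, in proportion to the Aim 2 share of the controls. It can create an effect or hide one, and the pooled test gives no sign of which has happened.

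The documents do not show that drift occurred, but they make it plausible. Section 2.1 mentions quality-improvement work on discharge communication at this hospital. Aim 1 asks about 20 providers from the same emergency department to review the concussion handout and discharge toolkit. Section 22.2.2 records pandemic changes to enrolment, without saying which cohort they affected. The interval between cohorts is unclear. Section 8.1 says it lists the aims in collection order and puts Aim 1 before Aims 2 and 3 together. Section 8.2 lists Aim 2, then Aim 1 (12 to 18 months), then Aim 3. The timeline itself is an attachment.

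The power statement in section 10.4 is a separate problem: it concerns another contrast and another outcome.

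**Working it through.** **Inputs from the documents.** 200 parents per cohort, 10% attrition and alpha 0.05 (section 10.4); 2:1 allocation in Aim 3 (section 5.2). Completers: 180 Aim 2 controls, 200 × 2/3 × 0.9 = 120 toolkit, 200 × 1/3 × 0.9 = 60 Aim 3 controls.

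**Assumptions, because the documents give no figure.** Two-sided tests; one binary outcome; Aim 3 control rate p of 40% or 50%; Aim 2 rate p − d, where d is the shift left after adjustment.

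**The plan's own figure.** Pooled-variance two-proportion test, 180 versus 180, 20-point difference: power is 99.8% (10% v 30%), 98.7% (20% v 40%), 97.5% (30% v 50%) and 96.9% (40% v 60%). The stated 98% is reproduced to within about a point, although it is not strictly a lower bound at mid-range rates.

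**Bias of the pooled contrast.** Aim 2 share = 180/(180 + 60) = 0.75. With no toolkit effect, the expected difference is p − [0.75(p − d) + 0.25p] = 0.75d. For d = 2, 5 and 10 points this is 1.5, 3.75 and 7.5 points.

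**Type I error, worked for p = 0.40, d = 0.05.**
- Pooled control rate = (180 × 0.35 + 60 × 0.40)/240 = 0.3625; bias = 0.0375.
- Overall rate = (87 + 48)/360 = 0.375.
- Null SE = √[0.375 × 0.625 × (1/240 + 1/120)] = 0.0541.
- True SE = √[(180 × 0.35 × 0.65 + 60 × 0.40 × 0.60)/240² + 0.40 × 0.60/120] = 0.0544.
- Rejection probability = Φ[(0.0375 − 1.96 × 0.0541)/0.0544] + Φ[(−0.0375 − 1.96 × 0.0541)/0.0544] = 0.108.

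The same formula gives, for p = 0.40 / 0.50:

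| Toolkit v (Aim 3 + Aim 2 controls) | Aim 2 share | d = 2 | d = 5 | d = 10 |
|---|---|---|---|---|
| 120 v (60 + 180), planned | 75% | 5.9% / 5.8% | 10.8% / 10.3% | 29.2% / 27.1% |
| 60 v (30 + 90), half size | 75% | 5.5% / 5.4% | 7.9% / 7.6% | 17.2% / 15.9% |
| 120 v (60 + 60) | 50% | 5.3% / 5.3% | 6.8% / 6.7% | 12.5% / 12.0% |

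At half size the bias is unchanged, because the share is unchanged. At a 50% share it is 1.0, 2.5 and 5.0 points. Simulation at planned size agreed within 0.4 points. The Aim 3-only test (120 v 60) simulated at 5.0% / 5.1% and does not depend on d.

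**Masking.** With a true 20-point effect at planned size, pooled power is 95.1% / 95.8% with no drift. It falls to 83.2% / 85.0% if Aim 2 is 5 points higher than Aim 3 controls, and to 61.1% / 63.7% if 10 points higher.

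**Section 10.4 contrast.** One third of Aim 3 are controls, so a 20-point toolkit effect appears between cohorts as 20 × 120/180 = 13.3 points. Power at 180 v 180 is then about 72-93% over base rates of 10-70%. A 20-point cohort difference would need a toolkit effect of 20/(2/3) = 30 points. The outcome is the reach measure, read here as the receipt of discharge components that 14.1 lists as secondary.

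**Precision (95% half-width, 50% rate).**
- Pooled, 120 v 240: 1.96 × √(0.25/120 + 0.25/240) = 11.0 points.
- Aim 3 only, 120 v 60: 1.96 × √(0.25/120 + 0.25/60) = 15.5 points.
- Aim 2 v Aim 3 controls, 180 v 60: 1.96 × √(0.25/180 + 0.25/60) = 14.6 points.

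**The case against.** **Pooling is inferred.** The sentence in 5.2 describes what control parents experience, and 14.1 never says that the controls are pooled. Section 1.1 also gives Aims 2 and 3 separate purposes. That is fair, and it limits confidence. But 5.2 assigns participants to intervention and control groups across both cohorts, 14.1 uses the same two labels, and nothing limits the primary test to Aim 3. The one alternative in the text, Aim 2 versus Aim 3 in 10.4, is also non-randomised.

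**The covariate rule might admit cohort.** Under pooling, cohort differs by treatment group by construction, so it could enter if associated with outcome. It is not named, however. If it did enter, nearly all the information on the toolkit effect would come from Aim 3, since Aim 2 has no toolkit parents. That would be a different analysis with different precision, so the plan should say which is meant. The named covariates may remove measured case-mix differences; they cannot be relied on to remove changes in usual care.

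**The sizes are illustrative.** This stands. The largest error rates need a 10-point residual shift at planned size, and the cover note reports a smaller sample. The calculation is unadjusted and covers one binary outcome, whereas 14.1 tests each behaviour and a total. The bias share is the firmer result.

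**The remedy is weak.** This stands in part. At planned size the drift check has only about 10-11% power for a 5-point shift and 28-30% for 10 points. Its interval still shows how much drift the data allow.

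**The power point is separate.** Agreed: it has its own fix and adds no weight to the pooling concern.

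**Conclusion.** The concern holds and should be fixed. On the plain reading, the primary result is a mostly non-randomised contrast, with no randomised estimate planned beside it although the randomised data are collected. At planned sizes 75% of any residual cohort shift passes into the estimate. The realised share is unknown. The error rates above depend on assumed shifts and control rates: modest for 2 points, about double the nominal level for 5, and more than five times it for 10 at planned size.

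Confidence is medium, because the pooling comes from reading sections 1.2, 5.2 and 14.1 together and the timeline was not available. Independently of that, the 10.4 statement fits neither the primary outcome nor the toolkit versus control contrast.

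**What to change.** In 14.1, state that the control group combines Aim 2 parents and Aim 3 controls, if that is intended. Beside the pooled result, report:

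1. the randomised Aim 3 toolkit versus control difference with its 95% CI, using the planned covariates;
2. the Aim 2 versus Aim 3-control difference with its 95% CI, without reading non-significance as absence of drift.

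Label both post hoc if outcomes have already been seen, and rest any claim of randomised evidence on the first.

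In 10.4, restate power for the toolkit versus control contrast analysed and name the outcome. If recruitment has ended, as the cover note suggests, give the CI half-width at the actual group sizes instead.

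The cost is wording in two sections and two extra estimates. The Aim 3-only estimate is less precise. At planned size its power for 20 points is about 72-90% over base rates of 10-70%, against 95-99.6% pooled with no drift. At half size its power is about 43-66% and its half-width about 21.9 points. It may be inconclusive alone; its use is to show how far the pooled result depends on the Aim 2 controls.
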